### **8.1.2 Post baseline**

- **Mammogram/breast MRI**

Mammogram (or breast MRI) will be performed on yearly basis from randomization (± 30 days), and as clinically indicated until the detection of locoregional recurrence and distant recurrences (whichever comes last) or end of follow-up period, whichever comes first.

- **CT Scan/MRI/Other imaging**

The post baseline imaging work-up will be done as clinically indicated until the detection of locoregional recurrence and distant recurrences (whichever comes last) or end of follow-up period.

The imaging work-up can include: Radionuclide Bone Scan Whole Body, CT Scan, MRI, PET-CT, Ultrasound of Chest, Abdomen, Pelvis or any clinically indicated sites of disease and clinical evaluation of superficial disease.

- **Biopsy**

Disease recurrence should be confirmed histologically whenever possible.

Note: for the locoregional recurrence including skin recurrence it is recommended to perform a biopsy unless clinically contra-indicated.

### **8.1.3 Overall survival follow-up**

After discontinuation of study treatment, follow-up visits will be performed every 12 months (±45 days) from the last dose of study treatment for survival status and collection of data on post-study anticancer therapies, and disease recurrence for patients who complete or prematurely discontinue study treatment without disease recurrence.

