NIMP: GnRH analog		↔							- Goserelin or other GnRH analog approved for use in early breast cancer as per site/ country availability - In men and pre/perimenopausal women

Procedure	Screening Period	Treatment Period [5 years – C1-C65]					EOT	Follow-up Period	Notes
		0	1	2	3	4-10 Q12 weeks			
Patient Visit #	Baseline	C1 D1	C2 D1	C4 D1	C7, C10, C13, C16, C19, C22, C25 D1	C28, C34, C40, C46, C52, C58 D1	D30 after last IMP dose	Q12 months after last IMP dose	
Patient Cycle Visit #	Up to 28 days before randomization	±3	±3	±7	±7	±7	±7	±45	
AE/SAE review	←=====→							X (ongoing related AEs, AESI, ongoing SAEs at EOT and new related AE/SAEs)	
Concomitant medication review	←=====→							X (related to AE/SAEs listed above)	From the date of informed consent form up to 30 days after the last dose of study treatment
Disease assessments:									
Disease recurrence assessment	X								At every visit and as clinically indicated until the detection of locoregional recurrence and distant recurrences (whichever comes last) or end of follow-up period, whichever comes first.

Procedure	Screening Period	Treatment Period [5 years – C1-C65]					EOT	Follow-up Period	Notes
		0	1	2	3	4-10 Q12 weeks			
Patient Visit #	Baseline	C1 D1	C2 D1	C4 D1	C7, C10, C13, C16, C19, C22, C25 D1	C28, C34, C40, C46, C52, C58 D1	D30 after last IMP dose	Q12 months after last IMP dose	
Patient Cycle Visit #	Up to 28 days before randomization	±3	±3	±7	±7	±7	±7	±45	
Time Window (day)									
Mammogram	X a				X b				
a. Screening: to be done if not already done in the past 6 months prior to randomization.
 
If local investigator plans to use MRIs instead of mammograms during the study, MRI will have to be performed at baseline
 
b. Post baseline: yearly from randomization (±30 days), and as clinically indicated until the detection of locoregional recurrence and distant recurrences (whichever comes last) or end of follow-up period, whichever comes first.

Procedure	Screening Period	Treatment Period [5 years – C1-C65]					EOT	Follow-up Period	Notes
		0	1	2	3	4-10 Q12 weeks			
Patient Visit #	Baseline	C1 D1	C2 D1	C4 D1	C7, C10, C13, C16, C19, C22, C25 D1	C28, C34, C40, C46, C52, C58 D1	D30 after last IMP dose	Q12 months after last IMP dose	
Patient Cycle Visit #	Up to 28 days before randomization	±3	±3	±7	±7	±7	±7	±45	
Time Window (day)									

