Radionuclide Bone Scan Whole Body; CT Scan / MRI /PET-CT Ultrasound of Chest, Abdomen, Pelvis or any clinically indicated sites of disease; Clinical evaluation of superficial disease	(X a )				(X b )				
a. Screening: to be done for patients at highest clinical risk for disease recurrence as outlined in I 08 (Section 5.1), for patients with stage IIIA or higher as clinically indicated.
 
b. Post baseline: to be done as clinically indicated until the detection of locoregional recurrence and distant recurrences (whichever comes last) or end of follow-up period, whichever comes first.

Biopsy (disease recurrence proof)					(X)				Disease recurrence should be confirmed histologically whenever possible. For the locoregional recurrence including skin recurrence it is strongly recommended to perform a biopsy unless clinically contra-indicated.

Procedure	Screening Period	Treatment Period [5 years – C1-C65]					EOT	Follow-up Period	Notes
		0	1	2	3	4-10 Q12 weeks			
Patient Visit #	Baseline	C1 D1	C2 D1	C4 D1	C7, C10, C13, C16, C19, C22, C25 D1	C28, C34, C40, C46, C52, C58 D1	D30 after last IMP dose	Q12 months after last IMP dose	
Patient Cycle Visit #	Up to 28 days before randomization	±3	±3	±7	±7	±7	±7	±45	
Time Window (day)									
Overall Survival Follow-up								X	After discontinuation of study treatment, post-study survival status (including post-study anticancer therapies; disease recurrence for patients who complete or prematurely discontinue study treatment without disease recurrence) will be collected
Electronic PRO measures:									
EORTC QLQ-C30, EORTC QLQ-BR23, EORTC-QLQ-IL127, EQ-5D-5L, PGIS		X a					X b		a. Data collected prior to first IMP intake on device at site on D1 C1 or earlier if patient has no unrecovered acute toxic effects of prior AI therapy (see exclusion criteria 6). b. At each visit after the 1 st cycle (D1 C2-C58) during the treatment period, at EOT, and at the first two post-treatment follow up visits. Data collected on device at site.

Procedure	Screening Period	Treatment Period [5 years – C1-C65]					EOT	Follow-up Period	Notes
		0	1	2	3	4-10 Q12 weeks			
Patient Visit #	Baseline	C1 D1	C2 D1	C4 D1	C7, C10, C13, C16, C19, C22, C25 D1	C28, C34, C40, C46, C52, C58 D1	D30 after last IMP dose	Q12 months after last IMP dose	
Patient Cycle Visit #	Up to 28 days before randomization	±3	±3	±7	±7	±7	±7	±45	
Time Window (day)									

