Time Window (day)		X a	X a				X b		Refer to Section 8.6.2 for details a. Pre-dose b. Collected at EOT for patients who discontinued treatment due to disease recurrence
(Optional) Blood Samples for Future Research									

All study visits performed during treatment period and follow-up period are conducted on-site (in participants without disease recurrence). On-site visits could be substituted by remote visits in specific circumstances.

**Screening:** Routine baseline tests performed prior to ICF signature do not need to be repeated as long as they are within the screening defined timeframe. Informed consent should be signed before any study specific procedures. It can be signed more than 28 days prior to randomization. Screening time indicates in which timeframe exams used to support eligibility have to be done prior to randomization.

**Randomization:** To take place once the consented patient has completed all the necessary screening procedures and is deemed eligible for study entry by the Investigator or designee. All eligible patients must be randomized using IRT. Every effort should be made to start treatment within 3 working days of randomization.

**Treatment period:** A cycle is defined as a 28-day period. Men and pre/perimenopausal women will receive GnRH analog on D1 of the cycle.

**Physical examination/ signs and symptoms evaluation:** At a minimum, assessments of the cardiovascular system, pulmonary system, gastrointestinal system (including palpation of liver and spleen), examination of the skin, and breast exam (palpation of breast/chest wall, axillae, supra- and infraclavicular regions). Symptom-directed physical examinations should be performed at screening and at each subsequent visit.

**Cycle 1 D1** refers to the day the patient receives the initial dose of IMP. Repeated evaluation of body weight, signs and symptoms, physical examination and laboratory tests is not necessary if performed within 7 days prior to 1st IMP administration. If evaluation performed during screening is abnormal, repeated evaluation is recommended within 2 days prior to 1st IMP administration.

**End of treatment (EOT):** should be performed 30 days (±7 days) after the last IMP and prior to the initiation of any new anti-cancer therapy, whichever comes first.

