## **DRFS**

DRFS is defined as the time from date of randomization to the date of the first occurrence of one of the following events:

- Distant recurrence: Metastatic disease-breast cancer that has either been biopsy confirmed or clinically diagnosed as recurrent invasive breast cancer.
- Death attributable to any cause, including breast cancer, nonbreast cancer, or unknown cause.

Same censoring rules as defined for the IBCFS will be used.

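### Section 8.1.3 and the SoA survival row conflict with Section 8.1.2 and the SoA disease-recurrence row on recording recurrence after a first relapse, which DRFS and LRRFS need

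*Combined protocol and SAP*

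**What the plan says.** **The narrow rule.** Protocol Section 8.1.3 schedules follow-up every 12 months after the last dose for survival status, later anticancer therapy, and "disease recurrence for patients who complete or prematurely discontinue study treatment without disease recurrence". The Overall Survival Follow-up row of the SoA (Section 1.3) carries the same limit: "disease recurrence for patients who complete or prematurely discontinue study treatment without disease recurrence) will be collected".

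**The broad rule.** The disease-recurrence row of the SoA requires assessment "At every visit and as clinically indicated until the detection of locoregional recurrence and distant recurrences (whichever comes last", or to the end of follow-up. Section 8.1.2 repeats this stopping rule for mammogram or breast MRI ("as clinically indicated until the detection of locoregional recurrence and distant recurrences (whichever comes last) or end of follow-up period, whichever comes first") and for other imaging ("The post baseline imaging work-up will be done as clinically indicated until the detection of locoregional recurrence and distant recurrences (whichever comes last"). The mammogram and imaging rows of the SoA match.

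**Where visits take place.** A note under the SoA reads: "All study visits performed during treatment period and follow-up period are conducted on-site (in participants without disease recurrence".

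**What the endpoints need.** DRFS counts distant recurrence or death from any cause. LRRFS counts ipsilateral, locoregional or contralateral invasive events, or death. For censoring, Section 9.2.3.2 says of each: "Same censoring rules as defined for the IBCFS will be used". Under Section 9.2.2, a participant without an event is censored at the last disease assessment showing none. An event documented more than 12 months + 90 days after the previous assessment is censored back to that assessment.

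**The concern.** Section 4.1 ends study treatment at recurrence as the IBCFS definition has it, and that definition includes locoregional and contralateral events. A participant who relapses on treatment therefore leaves treatment with recurrence and is outside the group in which 8.1.3 collects further recurrence. For DRFS these participants are still at risk: a locoregional or contralateral event is neither a DRFS event nor a reason to censor. LRRFS has the mirror problem after a first distant relapse.

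If data capture were built on 8.1.3, later DRFS and LRRFS events in these participants could go unrecorded. The lapse in assessment would be triggered by a breast cancer event, so the resulting censoring would be informative. Dates not collected prospectively may not be recoverable for the 5- and 10-year analyses.

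**Working it through.** The plan gives no DRFS event count or power to reproduce, so the check is mainly a comparison of passages.

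**Step 1. Follow each type of first event on treatment.**

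| First event | 8.1.3 and survival row | 8.1.2 and disease-recurrence row | Endpoint still open |
|---|---|---|---|
| Locoregional | survival and later therapy only | continue until distant recurrence is found | DRFS |
| Contralateral | survival and later therapy only, if it counts as recurrence | continue; it is not a stopping event | DRFS |
| Distant | survival and later therapy only | continue until locoregional recurrence is found | LRRFS |
| None when treatment stops | recurrence collected | continue | all |

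The rules differ in the first three rows, exactly where DRFS or LRRFS is still open. Section 8.1.3 does not say whether a contralateral cancer counts as recurrence; the IBCFS-based usage in Section 4.1 suggests that it does.

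**Step 2. Ask how the broad rule would operate.** It applies at every visit. The SoA note describes on-site visits only for participants without recurrence. No passage states how recurrence is assessed or recorded at follow-up contacts with the others.

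**Step 3. Apply the censoring rule.**
- Annual visits have a window of ±45 days, so consecutive visits can be 12 months + 45 + 45 = 12 months + 90 days apart. The limit equals the widest permitted gap and does no harm while assessments continue.
- Suppose the last disease assessment is the end-of-treatment visit, 30 ± 7 days after the last dose, and later contacts record survival only.
- First annual contact: the gap is at most 12 months + 45 − 23 = 12 months + 22 days, inside the limit. An event documented then would count.
- Second annual contact: the gap is at least 24 months − 45 − 37 = 24 months − 82 days, outside the limit. A distant relapse first documented then would be censored back to the end-of-treatment visit.
- Section 9.2.2 makes no exception for death, so on a literal reading a death after such a gap would be censored too.

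**Step 4. Bound the loss, by assumption only.** The documents give neither the mix of first events nor the rate of later distant relapse. Assume that 20–30% of the 568 planned IBCFS events are locoregional or contralateral, that 20–35% of those participants later relapse distantly, and that none of these relapses is captured.
- Low: 568 × 0.20 = 114; 568 × 0.20 × 0.20 = 23; share 23 / (568 − 114 + 23) = 23 / 477 = 5%.
- High: 568 × 0.30 = 170; 568 × 0.30 × 0.35 = 60; share 60 / (568 − 170 + 60) = 60 / 458 = 13%.

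This is a ceiling. It assumes that every site ignores the broad rule and gives no credit for deaths counted within the window. It also includes first events after treatment, although 8.1.3 defines its group by status when treatment stopped.

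**The case against.** The strongest reply is that the broad rule is plainly the intended one. Section 8.1.2 and three SoA rows state it, against one section and one row whose subject is survival follow-up. Section 8 makes adherence to the SoA essential. Section 7.1.1 keeps participants in the study for endpoint evaluation after treatment stops, Section 7.1.2 follows them under the protocol procedures, and the SoA notes run follow-up to 10 years without listing recurrence as a reason to end it.

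That reply stands as to intent and rules out several stronger readings:
- A reader might infer that the plan does not collect distant relapse after a local event. It does, under the broad rule; the fault is that other passages say otherwise.
- A reader might infer that DRFS is censored at the first local event. No rule says so. Informative censoring arises only if assessments lapse.
- A reader might take the on-site note to mean that relapsed participants have no visits. It concerns where visits take place, and 8.1.3 collects survival and later therapy without excluding them.
- A reader might take 5–13% as an expected loss. It rests on assumed rates and complete non-capture.

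The reply does not remove the conflict. A CRF designer or site working from 8.1.3 would have textual support for not recording these events.

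**Conclusion.** The conflict is real and should be resolved, but it is a conflict of wording and not a missing collection rule. If the broad rule is followed, little is lost. If the narrow rule governs data capture, DRFS and LRRFS may lose events in participants who have already relapsed, and the inherited 12 months + 90 days rule could censor later events, including deaths on a literal reading. The size cannot be derived from the documents; the 23 to 60 events are an assumption-based ceiling.

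The reach is limited. IBCFS and IDFS end at the first relapse, so neither depends on what is recorded afterwards. DRFS and LRRFS are other secondary endpoints with no statistical test, so type I error is unaffected. What is at stake is the completeness of two descriptive endpoints.

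**What to change.** Reconcile Section 8.1.3 and the SoA Overall Survival Follow-up row with Section 8.1.2 and the SoA disease-recurrence row. Replace the restriction with wording to this effect:

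- At each 12-monthly follow-up contact, on-site or remote, record for every participant the recurrence status, the date of assessment, and the date and site of any locoregional, contralateral or distant recurrence. Do this regardless of earlier events, until locoregional and distant recurrence are both documented or follow-up ends.
- In Section 9.2.3.2, state that such a contact counts as a disease assessment for DRFS and LRRFS censoring. The dates of negative assessments are needed as well as the dates of events; without them the 12 months + 90 days rule could still censor events that were collected.

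The cost is one additional CRF item at contacts already scheduled for survival and later therapy. No visit or imaging is added. The change should be made prospectively.

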## **8.2 SAFETY ASSESSMENTS**

Planned time points for all safety assessments are provided in the SoA ([Section 1.3](#)).

### 8.2.1 Physical examinations

- A physical examination should include, at a minimum, assessments of the cardiovascular system, pulmonary system, gastrointestinal system (including palpation of liver and spleen), examination of the skin, and breast exam (palpation of breast/chest wall, axillae, supra- and infraclavicular regions). Height (at baseline only) and weight will also be measured and recorded. Investigators should pay special attention to clinical signs related to previous serious illnesses.
- A gynecological examination should be performed at least on a yearly basis according to the schedule provided in the SoA (see Section 1.3), or more frequently in case of sign or symptoms of endometrial abnormality (eg, abnormal bleeding). The examination should be performed as per the site's local guidelines and the result should be reported as either normal or abnormal.
- Any new finding or worsening of previous finding should be reported as a new adverse event.

### 8.2.2 Vital signs

- Body temperature, blood pressure and pulse measurements will be assessed with a completely automated device. Manual techniques will be used only if an automated device is not available.
- Systolic and diastolic blood pressure, and pulse rate will be measured in a semi-supine position after 5 minutes rest.
- Single 12-lead ECG will be obtained as outlined in the SoA (see [Section 1.3](#)) using an ECG machine that automatically calculates the heart rate and measures PR, QRS, QT, and QTc intervals.
- Vital signs and ECG abnormalities are to be recorded as adverse events only if they are symptomatic and/or requiring corrective treatment and/or leading to treatment discontinuation and/or dose modification and/or fulfilling a seriousness criterion (see [Section 10.3](#) [Appendix 3]).

### 8.2.3 Clinical safety laboratory assessments

- See Appendix 2 ([Section 10.2](#)) for the list of clinical laboratory tests to be performed and to the SoA ([Section 1.3](#)) for the timing and frequency.
- The Investigator must review the laboratory report, document this review, and record any clinically relevant changes occurring during the study. The laboratory reports must be filed with the source documents. Clinically significant abnormal laboratory findings are those which are not associated with the underlying disease, unless judged by the Investigator to be more severe than expected for the participant's condition. Laboratory abnormalities are to be recorded as adverse events only if they lead to treatment discontinuation and/or dose modification and/or fulfill a seriousness criterion and/or are defined as an AESI (see [Section 10.3](#), [Appendix 3]).

- All laboratory tests with values considered clinically significantly abnormal during participation in the study or within 30 days after the last dose of study intervention should be repeated until the values return to normal or baseline or are no longer considered clinically significant by the Investigator or medical monitor.
  - If such values do not return to normal/baseline within a period of time judged reasonable by the Investigator, the etiology should be identified, and the Sponsor or Sponsor's representatives notified.
  - All protocol-required laboratory assessments, as defined in Appendix 2 ([Section 10.2](#)), must be conducted in accordance with the laboratory manual and the SoA ([Section 1.3](#)).
  - If laboratory values from non-protocol specified laboratory assessments performed at the institution's local laboratory require a change in participant management or are considered clinically significant by the Investigator (eg, SAE or AE or dose modification), then the results must be recorded in the CRF.

### **8.3 ADVERSE EVENTS (AES), SERIOUS ADVERSE EVENTS (SAES) AND OTHER SAFETY REPORTING**

AE will be reported by the participant (or, when appropriate, by a caregiver, surrogate, or the participant's legally authorized representative).

The Investigator and any qualified designees are responsible for detecting, documenting, and recording events that meet the definition of an AE or SAE and remain responsible for following up AEs that are serious, considered related to the study intervention or study procedures, or that caused the participant to discontinue the study intervention (see [Section 8.2](#)).

#### **8.3.1 Time period and frequency for collecting AE and SAE information**

All AEs and SAEs will be collected from the signing of the ICF at the time points specified in the SoA ([Section 1.3](#)) and until at least 30 days after administration of the last study intervention. After this period, all ongoing related AEs, all ongoing SAEs regardless of relationship with study treatment, and all new related AEs (serious or nonserious), are to be reported and followed up until resolution or stabilization. All SAEs and AESI will be recorded and reported to the Sponsor or Sponsor's representatives immediately and under no circumstance should this exceed 24 hours, as indicated in Appendix 3 ([Section 10.3](#)). The Investigator will submit any updated SAE data to the Sponsor within 24 hours of it being available.

Investigators are not obligated to actively seek AE or SAE after conclusion of the study participation. However, if the Investigator learns of any SAE, including a death, at any time after a participant has been discharged from the study, and he/she considers the event to be reasonably related to the study intervention or study participation, the Investigator must promptly notify the Sponsor.

### 8.3.2 Method of detecting AEs and SAEs

The method of recording, evaluating, and assessing causality of AE and SAE and the procedures for completing and transmitting SAE reports are provided in Appendix 3 ([Section 10.3](#)).

Care will be taken not to introduce bias when detecting AEs and/or SAEs. Open-ended and non-leading verbal questioning of the participant is the preferred method to inquire about AE occurrences.

